6.5. Contouring of normal tissue structures

6.5.1 Spinal Cord

The spinal cord will be contoured based on the bony limits of the spinal canal, starting at least 10 cm above the superior extent of the PTV and continuing on every CT slice to at least 10 below the inferior extent of the PTV.

6.5.2 Lung (Right & Left) minus GTV

Contour right and left lung as one structure including all parenchymal lung tissue but excluding the GTV and major airways (trachea and main/lobar bronchi).

6.5.3 Esophagus

The esophagus will be contoured using mediastinal windowing on CT to correspond to the mucosal, submucosa, and all muscular layers out to the fatty adventitia. The esophagus should be contoured starting at least 10 cm above the superior extent of the PTV and continuing on every CT slice to at least 10 below the inferior extent of the PTV.

6.5.4 Brachial Plexus

The defined ipsilateral brachial plexus originates from the spinal nerves exiting the neuroforamina on the involved side from around C5 to T2. For the purposes of this protocol, only the major trunks of the brachial plexus will be contoured. The brachial plexus will be contoured starting proximally at the neuroforamina, following along the route of the subclavian vein ending after it crosses the second rib.

6.5.5 Heart/Pericardium

The heart, along with the pericardial sac, should be contoured from its base to apex, beginning superiorly at the level of the inferior aspect of the aortic arch (aorto-pulmonary window) and extending inferiorly to the apex of the heart.

6.5.6 Great Vessels

Contour the wall and lumen of the named vessel at least 10 cm superior and inferior to PTV.

6.5.7 Trachea and Large Bronchus

Contour the trachea and cartilage rings starting 10 cm superior to the PTV extending inferiorly to the bronchi ending at the first bifurcation of the named lobar bronchus.

6.5.8 Rib

Contour each rib separately within 5 cm of the PTV in any direction.

6.5.9 Skin

The skin will be defined as the outer 0.5 cm of the body surface. As such it is a rind of uniform thickness (0.5 cm) which envelopes the entire body in the axial planes. The cranial and caudal surface of the superior and inferior limits of the planning CT should not be contoured as skin unless skin is actually present in these locations (e.g., the scalp on the top of the head.

6.6 Documentation Requirements

In general, treatment interruptions should be avoided by preventative medical measures and nutritional, psychological, and emotional counseling. Treatment breaks, including indications, must be clearly documented on the treatment record.

6.7 Compliance Criteria (both Arms A and B)

Planning Priorities:

1) Critical normal structure constraints (see sections 6.1.5 and 6.2.5): The spinal cord, brachial plexus, heart, and lung are considered critical normal structures and constraints on these structures will be prioritized. No plan will be accepted that exceeds the stated dosimetric goals for the spinal cord. If there is a need to drive dose to other normal structures, including lung, heart, etc., in order to not exceed spinal cord dose, this is acceptable as long as these changes in dose to other normal structures fulfills the protocol rules. Exceeding these limits for the brachial plexus, heart, or lung structures by more than 5% in any circumstance constitutes a minor protocol violation. Exceeding these limits by more than 10% constitutes a major protocol violation. It is understood that other normal structures dose limits would be exceeded in some patients because of their corresponding tumor distribution and meeting target coverage requirements. In general, when targets are within 1 cm of normal structures, attempts must be made to avoid exceeding constraints on these structures especially sparing of the contralateral wall to avoid circumferential radiation (see figure below, section 6.4.7)). Normal structures > 1 cm away from the target are subject to the above protocol violation description.

2) Variations of dose prescription:

No deviation: 95% of the PTV receives the prescribed dose, \geq 99% of the PTV receives \geq 90% of the prescribed dose, and a contiguous volume of no more than 2 cc anywhere within the patient receives \geq 110% of the prescribed dose.

Minor deviation: Deviations of this magnitude are not desirable, but are acceptable. 95% of the PTV receives < 100% but \geq 97% of the prescribed dose, \geq 99% of the PTV receives < 90% but \geq 87% of the prescribed dose, or a contiguous volume of no more than 2cc anywhere within the patient receives between 110-115% of the prescribed dose.

Major deviation: Doses in this region are not acceptable. 95% of the PTV receives < 97% of the prescribed dose, ≥ 99% of the PTV receives < 87% of the prescribed dose, or a contiguous volume of > 2cc anywhere within the patient receives ≥ 115% of the prescribed dose.

6.8 Radiation Quality Assurance Reviews

The Principal Investigator, [name], and Co-Chairs will perform a rapid review of the treatment plan for the first enrolled case from each institution prior to the institution delivering any protocol treatment. Institutions should allow 3 business days for each case to be received, processed, and reviewed. If the plan must be resubmitted, it will be given a rapid review (within 3 business days). Treatment plans for subsequent patients enrolled at a site will not be reviewed prior to delivery of treatment, but one may be requested by a site for helping with All de-identified plans, including the rapid review case, will be submitted compliance. electronically to the QA review co-PI, [name], at MD Anderson Cancer Center. The electronic submission process involves (1) the treatment plan (CT images, contours and dose distribution) which is deidentified; (2) the electronic data is sent to MD Anderson using an encrypted transmission (e.g. sFTP). The details of the software used for deidentification and transmission are determined based on the software/network of each institution. As part of image guidance used in the study, many sites will generate frequent cone-beam CT scans on the treatment unit. Although not mandatory, it is encouraged to send these de-identified images to [name] for secondary analysis of set up errors, etc.

The study PI and co-PIs will perform an RT Quality Assurance Review after complete data for the first 20 cases enrolled has been received. They will perform the next review after complete data for the next and subsequent 50 cases enrolled has been received. The final cases will be reviewed within 3 months after this study has reached the target accrual or as soon as complete data for all cases enrolled has been received, whichever occurs first.

6.9 Radiation Adverse Events

Adverse Events will be categorized and graded based primarily on the Common Toxicity Criteria for adverse events Version 4.0 (CTCAE version 4.0) with the exception of changes in pulmonary function tests (see section 6.9.4 below).

Radiotherapy should be interrupted for Grade 4 in-field toxicity and resumed when that toxicity has decreased to Grade ≤ 2 as detailed below. If treatment is interrupted for > two weeks, the patient should be removed from study treatment.

6.9.1 Reversible or permanent alopecia, bone marrow toxicity, skin pigmentation, and esophagitis are expected side effects of radiation therapy. Radiation induced myocarditis or transverse myelitis rarely occur at doses lower than 50 Gy. Radiographic evidence of radiation change and subsequent fibrosis of the lung will occur within lung volume receiving ≥20 Gy, usually within the first six months after initiation of treatment. It is essential to spare as much normal lung as possible in order to avoid symptomatic lung injury.

Adverse Event Monitoring

Adverse event data collection and reporting, which are required as part of every clinical trial, are done to ensure the safety of subjects enrolled in the studies as well as those who will enroll in future studies. Adverse events are reported in a routine manner at scheduled times during a trial. Additionally, certain adverse events must be reported in an expedited manner to allow for optimal monitoring of subject safety and care.

All subjects experiencing an adverse event, regardless of its relationship to study therapy, will be monitored until:

- the adverse event resolves or the symptoms or signs that constitute the adverse event return to baseline or is stable in the opinion of the investigator;
- > there is a satisfactory explanation other than the study therapy for the changes observed; or
- death.

Definitions

An adverse event is defined as any untoward or unfavorable medical occurrence in a human research study participant, including any abnormal sign (for example, abnormal physical exam, imaging finding or clinically significant laboratory finding), symptom, clinical event, or disease, temporarily associated with the subject's participation in the research, whether or not it is considered related to the subject's participation in the research.

Adverse events encompass clinical, physical and psychological harms. Adverse events occur most commonly in the context of biomedical research, although on occasion, they can occur in the context of social and behavioral research. Adverse events may be expected or unexpected.

Acute Adverse Events

Adverse events occurring in the time period from the signing of the informed consent, through 30 days post treatment will be considered acute adverse events.

Late Adverse Events (as applicable)

Adverse events occurring in the time period from the end of acute monitoring, to 2 years post treatment, will be defined as late adverse events. Only Radiation Oncology visits will be reviewed for adverse events.

Severity

Adverse events will be graded by a numerical score according to the defined NCI Common Terminology Criteria for Adverse Events (NCI CTCAE) Version 4.0. Adverse events not specifically defined in the NCI CTCAE will be scored on the Adverse Event log according to the general guidelines provided by the NCI CTCAE and as outlined below.

- Grade 1: Mild
- Grade 2: Moderate
- Grade 3: Severe or medically significant but not immediately life threatening
- Grade 4: Life threatening consequences
- Grade 5: Death related to the adverse event

Serious Adverse Events

ICH Guideline E2A and the UTSW IRB define serious adverse events as those events, occurring at any dose, which meets any of the following criteria:

- Results in death
- Immediately life-threatening
- Results in inpatient hospitalization^{1,2} or prolongation of existing hospitalization
- Results in persistent or significant disability/incapacity
- Results in a congenital anomaly/birth defect
- Based upon appropriate medical judgment, may jeopardize the subject's health and may require medical or surgical intervention to prevent one of the other outcomes listed in this definition.

Note: A "Serious adverse event" is by definition an event that meets *any* of the above criteria. Serious adverse events may or may not be related to the research project. A serious adverse event determination does not require the event to be related to the research. That is, both events completely unrelated to the condition under study and events that are expected in the context of the condition under study may be serious adverse events, independent of relatedness to the study itself. As examples, a car accident requiring ≥24 hour inpatient admission to the hospital would be a serious adverse event for any research participant; likewise, in a study investigating end-stage cancer care, any hospitalization or death which occurs during the protocol-specified period of monitoring for adverse and serious adverse events would be a serious adverse event, even if the event observed is a primary clinical endpoint of the study.

¹Pre-planned hospitalizations or elective surgeries are not considered SAEs. Note: If events occur during a pre-planned hospitalization or surgery, that prolong the existing hospitalization, those events should be evaluated and/or reported as SAEs.

² NCI defines hospitalization for expedited AE reporting purposes as an inpatient hospital stay equal to or greater than 24 hours. Hospitalization is used as an indicator of the seriousness of the adverse event and should only be used for situations where the AE truly fits this definition and NOT for hospitalizations associated with less serious events. For example: a hospital visit where a patient is admitted for observation or minor treatment (e.g. hydration) and released in less than 24 hours. Furthermore, hospitalization for pharmacokinetic sampling is not an AE and therefore is not to be reported either as a routine AE or in an expedited report.

Unanticipated Problems Involving Risks to Subjects or Others (UPIRSOs):

The phrase "unanticipated problems involving risks to subjects or others" is found, but not defined in the HHS regulations at 45 CFR 46, and the FDA regulations at 21 CFR 56.108(b)(1) and 21 CFR 312.66. For device studies, part 812 uses the term unanticipated adverse device effect, which is defined in 21 CFR 812.3(s). Guidance from the regulatory agencies considers unanticipated problems to include any incident, experience, or outcome that meets ALL three (3) of the following criteria:

Unexpected in terms of nature, severity or frequency given (a) the research procedures that are
described in the protocol-related documents, such as the IRB-approved research protocol and
informed consent document; and (b) the characteristics of the subject population being studied;

AND

Related or possibly related to participation in the research (possibly related means there is a
reasonable possibility that the incident, experience, or outcome may have been caused by the
procedures involved in the research);

AND

• Suggests that the research places subjects or others at greater risk of harm (including physical, psychological, economic, or social harm) than was previously known or recognized. Note: According to OHRP, if the adverse event is serious, it would always suggest a greater risk of harm.

Follow-up

All adverse events will be followed up according to good medical practices.

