All SAE/UPIRSOs at all sites, which occur in research subjects on protocols for which the SCCC is the DSMC of record require reporting to the DSMC regardless of whether IRB reporting is required. All SAEs/UPIRSOs occurring during the protocol-specified monitoring period should be submitted to the SCCC DSMC within 5 business days of the PI or delegated study team members awareness of the event(s). In addition, for participating centers other than UTSW, local IRB guidance should be followed for local reporting of serious adverse events.

The UTSW study team is responsible for submitting SAEs/UPIRSOs to the SCCC DSMC Coordinator. Hardcopies or electronic versions of the eIRB Reportable Event report; FDA Form #3500A forms, or other sponsor forms, if applicable; and/or any other supporting documentation available should be submitted to the DSMC Coordinator. The DSMC Coordinator forwards the information onto the DSMC Chairman who determines if immediate action is required. Follow-up eIRB reports, and all subsequent SAE/UPIRSO documentation that is available are also submitted to the DSMC Chair who determines if further action is required. (See Appendix III of the SCCC DSMC Plan for a template Serious Adverse Event Form which may be utilized when a sponsor form is unavailable and SAE submission to the eIRB is not required).

If the event occurs on a multi-institutional clinical trial coordinated by the UTSW Simmons Comprehensive Cancer Center, the DOT Manager or lead coordinator ensures that all participating sites are notified of the event and resulting action, according to FDA guidance for expedited

reporting. DSMC Chairperson reviews all SAEs/UPIRSOs upon receipt from the DSMC Coordinator. The DSMC Chairperson determines whether action is required and either takes action immediately, convenes a special DSMC session (physical or electronic), or defers the action until a regularly scheduled DSMC meeting.

Written reports to:

UTSW Clinical Research Manager

Email: [contact]

UTSW Institutional Review Board (IRB)

Submit a Reportable Event via eIRB with a copy of the final sponsor report as attached

supporting documentation

Reporting Unanticipated Problems Involving Risks to Subjects or Others (UPIRSOs) to the UTSW HRPP/IRB

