9.8 Cost-Effectiveness

Health care utilization data needed to assess costs will be obtained at the baseline visit (for the prior one year period) and at each follow-up visit (see Appendix II). Questions will be asked for the utilization of all the health care services (see Appendix VI). The health utilization data will be collected at each study site. They will be transferred to the data management center located at the Department of Epidemiology and Biostatistics, Texas A&M Health Science Center (TAMHSC). At TAMHSC, a designated staff member will be responsible for calling each health service provider and obtain the bills that are associated with each service reported in the CRF, with costs calculated using methods outlined below and stored in a designated computer for analysis purpose. Patients will be given a diary at the beginning of the study to aid in recording all health related visits and expenditures. Additionally, in order to assess the treatment related indirect costs and patient out of pocket costs, a form will be administered during the last week of treatment or at the first available follow up visit after completion of radiation treatment (see Appendix VII).

Hospitalizations: Inpatient admissions (hospitalizations for any reason) with dates of admission and discharge and name of hospital. Patient bills (UB-04s) also will be obtained for each hospitalization. Inpatient facility costs will be estimated by total billed charges adjusted by a facility-specific cost-to-charge ration from Medicare Cost Reports. We also will attempt to obtain billing records for inpatient physician services. For hospitalizations with physician billing records, impatient physician costs will be estimated by applying Medicare payment rates under the RBRVS-based Medicare Fee Schedule to billed procedures in the physician billing records. For hospitalizations where physician billing records are not available, inpatient physician costs will be estimated using a multivariate regression model from data that combines Medicare inpatient and physician bills. This is to

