be accomplished by merging the Medicare Provider Analysis and Review (MEDPAR) data set (a file that contains a record for each discharge of a Medicare beneficiary) and the 5 percent sample file of Medicare claims for physician services in the Medicare Beneficiary Survey. We will calculate the ratio between hospital costs and physician-allowable charges. Separate regression models will be estimated for all lung-related admissions (e.g., DRG 082) and for all other admissions. These regression models will be used to predict the ratio of inpatient physician costs to hospital costs for each admission. This predicted ratio multiplied by the hospital costs will be the estimated physician costs for the admission, but only for admissions without inpatient billing information.

Treatment Cost: Direct costs of radiation treatment including consultation, simulation, treatment planning, and treatment delivery. Patient bills related to treatment will be obtained and estimated by total billed charges adjusted by facility-specific cost-to-charge ration from Medicare cost reports as described above.

Emergency Room visits: The date of ER visit and name of the facility, and whether the ER visit resulted in a hospital admission. ER costs will be estimated using Medicare average payment rates for facility and physician charges, using the merged MEDPAR and MBS data as described above.

Physician and Clinic Visits: The date of the visit, the name of the physician or physician clinic, and the service provided (physician exam, lab test, physical therapy, etc.). Costs for physician and clinic visits will be calculated based on billing records obtained for such visits, using Medicare payment rates for procedures indicated in the clinic billing records.

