11.1.2.4 Toxicity: Grade 3-5 adverse events as graded by CTCAE v 4.0

11.2 Sample Size Determination

The sample size calculation is based on the primary endpoint, overall survival at 1 year, and the assumption that patients are randomized until the end of accrual. The sample size is calculated with the 2-sided significance level of 0.05 and 80% statistical power using a 2-sample log rank test. We assume that the overall survival function follows an exponential distribution for each arm. Accrual to the study is assumed to be uniformly distributed. The null hypothesis is that the there are no difference in 1-year survival rates between two arms. We assume that the patients will be accrued for 2 years with a 1-year follow-up. We hypothesize that the patients randomly assigned to the control arm and experimental arm have a 1-year survival rate of 45% (hazard rate [λc]) of 0.799) and 60% (hazard rate [λe]) of 0.511), respectively, which is translated to the hazard ratio of $\lambda e/\lambda c = 0.640$. One interim analysis and a final analysis are planned for early stopping for efficacy. The efficacy testing is based on the Lan-DeMets spending function, which resembles the O'Brien-Fleming boundary. The total sample size of 226 patients (113 in the control arm and 113 in the experimental arm) will be accrued to achieve the desired 80% statistical power and 2-sided significance level of 0.05. Guarding against ineligibility or lack-ofdata rate of up to 5%, the final targeted accrual for this study will be 238 patients (119 per arm). Sample size was estimated using the sample size software EaST version 5.

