11.5.7 Toxicity

Any subject who receives treatment on this protocol will be evaluable for toxicity. Each patient will be assessed for the development of toxicity according to the Time and Events table (Appendix II). Toxicity will be assessed according to the NCI Common Toxicity Criteria for Adverse Events (CTCAE), version 4.0. Dose adjustments should be made according to the system showing the greatest degree of toxicity.

Only adverse events assessed to be definitely, probably, or possibly related to protocol treatment will be considered. The rates of all Grade 3-5 adverse events, and death during or within 30 days of discontinuation of protocol treatment will be tested for equality using a two-sided chi-square test with a 0.05 significance level.

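### Late adverse events are reviewed only from Radiation Oncology visits, so severe events treated elsewhere can be missed, although the trial already records reported admissions and ER visits for costing

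*Combined protocol and SAP*

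**What the plan says.** Section 6.9.1 sets the late window: "Adverse events occurring in the time period from the end of acute monitoring, to 2 years post treatment, will be defined as late adverse events". Acute monitoring ends 30 days after treatment. The next sentence restricts the source: "Only Radiation Oncology visits will be reviewed for adverse events". It stands under the late-event heading, so the natural reading is that it governs late events only.

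Those events feed a secondary endpoint, listed in 11.1.2.4 as "Toxicity: Grade 3-5 adverse events as graded by CTCAE v 4.0". Section 11.5.7 has the rates "tested for equality using a two-sided chi-square test with a 0.05 significance level", after an attribution filter: "Only adverse events assessed to be definitely, probably, or possibly related to protocol treatment will be considered".

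For costs, Section 9.8 collects at each follow-up visit "Inpatient admissions (hospitalizations for any reason) with dates of admission and discharge and name of hospital" and, for emergency care, "The date of ER visit and name of the facility, and whether the ER visit resulted in a hospital admission". Appendix VI is the form. Hospital bills are then requested from the providers for the services reported. No section sends any of this to adverse event review.

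Safety reporting is a separate route. Hospitalization makes an event serious (6.9.1), late events attributed to treatment must be reported (6.10), and 6.11 adds: "All SAEs/UPIRSOs occurring during the protocol-specified monitoring period should be submitted to the SCCC DSMC within 5 business days", counted from when the investigator or study team becomes aware of the event.

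**The concern.** Radiation pneumonitis is one of the two toxicities that Section 9.9 names as primary, and 6.9.3 places its onset weeks to months after treatment, so it can fall in the late window. A patient with acute breathlessness may well go to the nearest hospital rather than to the Radiation Oncology clinic. Section 7.0 also allows adjuvant chemotherapy in both arms, so some patients will be under another service.

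If the rule is followed literally, such an episode enters the toxicity data only if it surfaces at a Radiation Oncology visit. The cost database could then hold an admission that the safety database lacks. At stake are the grade 3-5 comparison, where Section 9.9 itself says hypofractionation may increase normal tissue toxicity, and the completeness of what reaches the DSMC.

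**Working it through.** **1. Does any section close the gap?**

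| Section | What it provides | Finds an event treated elsewhere? |
|---|---|---|
| 6.9.1 | Review of Radiation Oncology visits | Only if raised at the visit |
| 6.10, 6.11 | Duty to report SAEs and attributed late events | No; it starts at awareness |
| 9.6.2 | Survival follow-up and effort to document cause of death | Fatal events only; admissions not mentioned |
| 9.8, Appendix VI | Reported admissions and ER visits with date and facility; bills | Yes, if reported, but used only for costs |

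**2. What the cost record can and cannot do.** Appendix VI asks for hospital, date and length of stay, but no diagnosis. It flags an admission; it does not grade or attribute it. Bills are sought for services already reported, so they add detail to a reported admission but do not reveal an unreported one.

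**3. Patients who die between visits.** Follow-up visits in the late window are 2 months apart (month 1 to 3), then 3 months apart to month 12, then 4 months apart in year 2 (Section 10.0, Appendix II). With the annual hazards in 11.2 (0.799 control, 0.511 experimental), the probability of dying within an interval of t years for a patient alive at its start is 1 - exp(-hazard × t):

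| Interval | Control | Experimental |
|---|---|---|
| 2 months | 1 - exp(-0.133) = 12% | 1 - exp(-0.085) = 8% |
| 3 months | 1 - exp(-0.200) = 18% | 1 - exp(-0.128) = 12% |
| 4 months | 1 - exp(-0.266) = 23% | 1 - exp(-0.170) = 16% |

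These patients complete no further worksheet, so reconciliation at follow-up visits alone would not reach them.

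**4. Effect on a recorded rate.** The plan gives no figure for the toxicity comparison. Recorded rate = true rate × capture. Both inputs are assumptions.

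- True 15%: 0.15 × 0.80 = 12%; 0.15 × 0.60 = 9%.
- For scale, Section 1.2 reports 4 patients with grade 3 or higher treatment-related toxicity among 52 in the dose-escalation trial (4/52 = 7.7%; the dose-level counts there sum to 62, giving 4/62 = 6.5%). At 7.7%, 60-80% capture gives 4.6-6.2%.

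**5. Effect on the comparison.** The arm size is the plan's 113 (11.2). That figure reproduces: 158 events for a hazard ratio of 0.640, two-sided 0.05 and 80% power; mean event probability 0.700 with 2 years' accrual and 1 year's follow-up; 158/0.700 = 225.8, so 226 in total. For two proportions with pooled variance under the null,

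power = Φ{[d - 1.96·√(2·p̄(1-p̄)/n)] / √([p₁(1-p₁) + p₂(1-p₂)]/n)}, n = 113, d = p₂ - p₁.

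| Capture, both arms | Recorded rates (assumed true 15% vs 30%) | Difference | Power |
|---|---|---|---|
| 100% | 15% vs 30% | 15 points | 77% |
| 80% | 12% vs 24% | 12 points | 65% |
| 60% | 9% vs 18% | 9 points | 51% |

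For assumed true rates of 10% vs 25%, power goes 85%, 74%, 60%; for 20% vs 35%, it goes 72%, 59%, 45%. If capture differed by arm (assumed 90% vs 70%, true 20% in both), the recorded rates would be 18% and 14%: a false 4-point difference, declared significant in that direction about 13% of the time.

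These figures apply the capture fraction to the whole grade 3-5 rate. Section 11.5.7 does not separate late from acute events, and the restriction concerns late ones, so the effect is diluted to the extent that acute events make up the total.

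**The case against.** The strongest reply is that the sentence describes routine review and not the whole safety system. A reader might infer that 6.9.1 contradicts 6.11. It does not: 6.11 is triggered by awareness, and 6.10 requires attributed late events to be reported wherever they were treated. A site can follow all three sections. That part of the reply stands. What it leaves open is how the team becomes aware of an outside event.

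A second reply is that history, adverse event evaluation and the worksheet fall at the same visits, so an admission remembered for one can be mentioned for the other. This is fair, and it is why events can be missed rather than will be. But the worksheet asks directly about admissions and ER visits and is supported by a patient diary (9.8), whereas the adverse event review has no such prompt.

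A third reply is that a pneumonitis admission followed by death before the next visit is not simply lost. Survival is tracked, cause of death is sought (9.6.2), and death and hospitalization are SAE criteria. This also stands. The weakness lies in grade 3-4 events and in attributing grade 5. The worksheet alone would not cure that case, so a check at death is needed.

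Finally, only treatment-related events count under 11.5.7, so many flagged admissions would drop out. That limits the yield, but attribution should follow detection.

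**Conclusion.** The point holds as a gap in ascertainment. The plan restricts the source of late adverse events, holds a second source that would flag outside events, and does not connect the two. The bias in recorded grade 3-5 rates is downward; with similar capture in both arms, a real difference is pulled towards zero.

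The size is unknown. Neither the 15% rate nor the 60-80% capture comes from the documents, so 9-12% is an illustration and should not be read as an estimate. Nothing in the documents shows that capture would differ by arm. Nor do they support saying that the DSMC will not see serious events: that applies only to events nobody on the team learns of.

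This is a cheap improvement. It bears on the secondary toxicity endpoint and safety monitoring, and leaves overall survival and the sample size untouched.

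**What to change.** Replace the restricting sentence in 6.9.1 with wording such as: *Late adverse events will be ascertained from Radiation Oncology visits and from every hospitalization and ER visit reported on the Appendix VI worksheet or shown in bills obtained under Section 9.8.*

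Add two steps:

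- At each follow-up, the site reconciles reported admissions and ER visits with the AE/SAE log, obtains source records for any without an entry, and grades and attributes them.
- At death, the same check is made once more, alongside the cause-of-death documentation in 9.6.2.

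No new tests or patient forms are needed. The cost is modest coordinator time, though more than reading a completed form: Appendix VI has no diagnosis field, so flagged admissions need outside records. The worksheet is collected at the sites, but the bills go to the separate economics centre (9.8, 10.0), so a return path is needed. That centre already plans to model lung-related admissions separately from others (9.8), which would help decide which records to request first.
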